3.5.1 Primary Completion

The primary study will completed after 15 months.

3.5.2 Study Completion

The study will completed after 15 months.

4 Study Enrollment and Withdrawal

4.1 Eligibility Criteria

4.1.1 Inclusion Criteria

Individuals must meet all of the following inclusion criteria in order to be eligible to participate in the study:

1. Provide signed and dated informed consent form
2. Be conscious, willing and able to comply with all study procedures and be available for the duration of the study
3. Female, at least 21 years old
4. Be scheduled for a breast biopsy (BIRAD 4, 4A, 4B, 4C or 5)
5. Patient with an at least 1 cm mass located at <3cm depth, approachable by 2.5 inch needle
6. Be medically stable as determined by the investigator
7. If a female of child-bearing potential, must have a negative urine pregnancy test within 24 hours prior to administration of Definity.

4.1.2 Exclusion Criteria

An individual who meets any of the following criteria will be excluded from participation in this study:

1. Males
2. Females who are pregnant or nursing
3. Patients who are medically unstable, patients who are seriously or terminally ill, and patients whose clinical course is unpredictable. For example:
 - a. Patients on life support or in a critical care unit.
 - b. Patients with unstable occlusive disease (e.g., crescendo angina).
 - c. Patients with clinically unstable cardiac arrhythmias, such as recurrent ventricular tachycardia.

- d. Patients with uncontrolled congestive heart failure (NYHA Class IV).
 - e. Patients with recent cerebral hemorrhage.
 - f. Patients who have undergone surgery within 24 hours prior to the study sonographic examination.
4. Patients with known hypersensitivity or allergy to any component of Definity.
 5. Patients with unstable cardiopulmonary conditions or respiratory distress syndrome.
 6. Patients with uncontrollable emphysema, pulmonary vasculitis, pulmonary hypertension or a history of pulmonary emboli.

4.2 Gender/Minority/Pediatric Inclusion for Research

We include only female 21 years of age or older regardless of race and speaking language. Since this study does not provide direct benefit to subjects, we determined the age limit of 21 so no state law requires parent's consent for our subject to participate in the study. In 2019, an estimated 268,600 new cases of invasive breast cancer are expected to be diagnosed in women while about 2,670 new cases of invasive breast cancer are expected to be diagnosed in men. The lifetime risk (up to age 95 and older) of breast cancer for women in US is about 13%. However, this risk varies by race and ethnic group: white- 13%, Black- 12%, Asian/Pacific Islander- 11%, Hispanic- 10%, American Indian/Alaska Native- 8%.

4.3 Strategies for Recruitment and Retention

Subjects eligible for trial enrollment will be identified by the investigators from the TJU patient population who are scheduled for a breast biopsy. An investigator or research coordinator will explain the study to the patient. The patient will be given time to consider the risks and benefits of the study and ask questions about participation. The consent form will be reviewed with the patient and then the patient will be given the form to review. If consent interview is conducted by a coordinator, a study investigator will then discuss the study with the subject and answer any additional questions. The patient, person conducting study interview (if applicable), and a study investigator will all sign the consent form. The patient will be given a copy of the signed consent form for her records.

Screening assessments will be performed within 24 hours prior to the administration of Definity. Trial participants will have the presence of inclusion criteria and absence of exclusion criteria verified by providing a medical history. A full demographic profile, known drug allergies or intolerances, and a review of the subject's medical/surgical history will be recorded. If the subject is a woman of childbearing potential, she will have a urine pregnancy test (the results of which will be made available to the subject prior to study initiation).

4.4 Participant Withdrawal

4.4.1 Reasons for Withdrawal

Participants are free to withdraw from participation in the study at any time upon request.

An investigator may terminate a study participant's participation in the study if:

- Any clinical adverse event (AE), laboratory abnormality, or other medical condition or situation occurs such that continued participation in the study would not be in the best interest of the participant.
- The participant meets an exclusion criterion (either newly developed or not previously recognized) that precludes further study participation.

4.4.2 Handling of Participant Withdrawals and Participant Discontinuation of Study Intervention

The date the subject is withdrawn from the trial and the reason for discontinuation will be recorded on the CRF. If a subject's participation in the trial is interrupted for any reason (e.g., because of an AE) and the subject has met the criteria described above for completing the trial, the subject's trial participation will be considered completed. If a subject's trial participation is interrupted for any reason by the subject's or investigator's choice and the subject has not met all of the criteria listed above, then the subject will be considered as an incomplete participant.

4.5 Premature Termination or Suspension of Study

This study may be suspended or prematurely terminated if there is sufficient reasonable cause. Written notification, documenting the reason for study suspension or termination, will be provided by the suspending or terminating party to investigators, funding agency, the Investigational New Drug (IND) sponsor, and regulatory authorities. If the study is prematurely terminated or suspended, the principal investigator will promptly inform the IRB and will provide the reason(s) for the termination or suspension.

Circumstances that may warrant termination include, but are not limited to:

- Determination of unexpected, significant, or unacceptable risk to participants.
- Insufficient adherence to protocol requirements.
- Data that is not sufficiently complete and/or evaluable.
- Determination of futility.

5 Study Intervention

5.1 Study Product

This study uses the ultrasound contrast agent, Definity (Lantheus Medical Imaging, Billerica, MA).

5.2 Study Product Description

Definity is a sterile, injectable cardiovascular ultrasound contrast agent comprised of lipid-coated echogenic microbubbles (majority diameter of 1-4 micrometers) filled with octafluoropropane gas and approved by the FDA for use in cardiology.

5.2.1 Acquisition

Definity will be provided by Lantheus, the manufacturer, directly to Thomas Jefferson University.

5.2.2 Formulation, Packaging, and Labeling

Component	Concentration	Chemical Abstracts Service
Glycerin	>10%	56-81-5
Lipid Blend SG896	<1%	N/A
Water	>50%	7732-18-5
Perfluoropropane	<1%	76-19-7
Propylene Glycol	>1%	57-55-6
Sodium Chloride	<1%	7647-14-5
Disodium orthophosphate	<1%	7782-85-6
Sodium phosphate monobasic	<1%	10049-21-5

Definity is supplied as a single use 2 ml clear glass vial containing clear liquid in packages of 4 and 16 single-use vials. It is labeled for the use in patients with suboptimal echocardiograms to opacity the left ventricular chamber and to improve the delineation of the left ventricular endocardial border. In this study, Definity will be used off-label with FDA approval under an IND (no. 112,241).

5.2.3 Product Storage and Stability

Definity needs to be stored between 2-8°C (36°-46°F). The microbubbles are stable and it is necessary to activate them before use.

5.3 Dosage, Preparation, and Administration

Definity will be at room temperature to warm before starting the activation procedure. Definity will be activated by shaking the vial for 45 seconds using the VIALMIX® apparatus (Lantheus Medical Imaging, North Billerica, MA) as suggested by the manufacturer. Two vials of Definity (3 ml in total) suspended in 50 ml saline will be administered as an IV infusion via a peripheral vein (preferably the antecubital vein), with infusion rates of 4 to 10 ml/min (titrated to effect).

5.4 Dose Modifications and Dosing Delays

The recommended infusion dose for the labeled echocardiograms is 1.3 ml and it was modified to 3 ml for this study in accordance with our prior experience in CEUS studies [Sridharan et al. 2013, Nam et al. 2017]. This dose typically provides 5 to 8 minutes of enhancement. Definity is reported to be well tolerated by patients. The largest safety studies published to date on the use of ultrasound contrast agents in humans (involving up to 4,300,966 subjects) concluded that these agents have a good safety profile in both cardiac and abdominal ultrasound applications [Main et al. 2009, Dolan et al. 2009, Wei et al. 2008]. However, as rare but serious cardiopulmonary reactions have been reported following the IV administration of Definity, all subjects will be monitored by a physician during the entire imaging period (as recommended by the FDA).

5.5 Study Product Accountability

The agent will be stored in a secure refrigerator, with only the study investigators and research personnel having access. The study researchers will be responsible for inventory control. The manufacturer will distribute Definity directly to TJU. Any unused product will be disposed at the study site.

5.6 Dietary Restrictions

There is no dietary restrictions for the study.

5.7 Administration of Procedural Intervention

Definity will be administered as an IV infusion via a peripheral vein (preferably the antecubital vein), with infusion rates of 4 to 10 ml/min (titrated to effect) through an 18 to 22 gauge angio-catheter.

5.8 Procedures for Training of Clinicians on Procedural Intervention

The staff in this study are trained for the administration of Definity from our previous studies. If there are clinicians who are not familiar with Definity, we will train them before their participation in the study. If the last training case is found appropriate, the clinical site will be allowed to proceed with the study and training cases will be included in the study analysis. If not, the site personnel will be re-trained.

5.9 Assessment of Clinician and/or Participant Compliance with Study Procedural Intervention

The assessment of clinician and participant compliance with the procedural intervention will be subject to a strict QA review by the study coordinator and investigators at TJU.

6 Study Schedule

6.1 Pretreatment Period/Screening

Patients will be identified and approached from TJU Breast Imaging Center (by investigators). An investigator or research coordinator will explain the study to the patient. The patient will be given time to consider the risks and benefits of the study and to ask questions about participation. A consent form will be reviewed with the patient.

Study participants will have the presence of inclusion criteria and absence of exclusion criteria verified by providing a medical history. A full history and physical examination will be obtained from the patient's referring physician. If the history and physical examination note does not provide adequate information about the patient, the subjects will be assessed for their eligibility by their referring physician before enrollment into the study. If the subject is a woman of childbearing potential, she will have a urine pregnancy test 24 hours prior to the CEUS study (the results of which will be made available to the subject prior to study initiation).

6.2 Enrollment/Baseline

Enrollment/ Visit day (before a biopsy)

- Obtain and document consent from participant on study consent form.
- Verify inclusion/exclusion criteria.
- Obtain demographic information, medical history, and medication history.
- Obtain the previous results of physical and imaging tests if available.
- If woman of childbearing potential, urine pregnancy test within 24 hours prior to receiving Definity (CEUS exam)

6.3 Treatment Period

On the visit day

- Perform Baseline Ultrasound imaging.
- Administer Definity (IV infusion)
 - Determine the optimized acoustic settings for 3D SHAPE imaging
 - Perform CEUS exam and collect 3D SHAPE data

- Wait for clearance of Definity
 - Collect 3D SHAPE data
- Local anesthesia procedures will be performed using simple Lidocaine 1%, or combined with 1:100,000 Epinephrine (EPI) before the IFP measurements.
- Take a single IFP measurement each from the breast tumor and its surrounding tissue using Stryker compartment pressure monitoring system with ultrasound imaging guide

Participants will be monitored for 30 minute following the administration of Definity.

6.4 End of Treatment Study Procedures

We will collect the results from a breast biopsy obtained as standard of care.

6.5 Withdrawal Visit/Discontinuation of Therapy

If participant withdraws early or investigator terminates participant's participation, no additional visits or evaluations will be required or offered to the participant.

7 Study Procedures and Evaluations

7.1 Study Procedures/Evaluations

- Ultrasound, without contrast
- Definity administration
- CEUS exam
- IFP measurements

7.2 Laboratory Procedures/Evaluations

7.2.1 Clinical Laboratory Evaluations

There is no clinical laboratory procedure for this study, except for the urine pregnancy test for women of childbearing potential. We will only collect the results from histology, pathology, and imaging provided as standard of care to evaluate the malignancy of the breast tumor.

8 Evaluation of Safety

8.1.1 Unanticipated Problems

Unanticipated problems (UAPs) include, in general, any incident, experience, or outcome that meets the following criteria:

- unexpected in terms of nature, severity, or frequency given (a) the research procedures that are described in the protocol-related documents, such as the IRB-approved research protocol and informed consent document; and (b) the characteristics of the participant population being studied;

UAPs are considered to pose risk to participants or others when they suggest that the research places participants or others at a greater risk of harm (including physical, psychological, economic, or social harm) than was previously known or recognized.

8.1.2 Adverse Events

An adverse event is any untoward or unfavorable medical occurrence in a human participant, including any abnormal sign (for example, abnormal physical exam or laboratory finding), symptom, or disease, temporally associated with the participant's participation in the research, whether or not considered related to the participant's participation in the research.

8.1.3 Serious Adverse Events

A serious adverse event (SAE) is one that meets one or more of the following criteria:

- Results in death
- Is life-threatening (places the participant at immediate risk of death from the event as it occurred)
- Is disabling or incapacitating
- Results in inpatient hospitalization or prolongation of existing hospitalization
- Results in a persistent or significant disability or incapacity
- Results in a congenital anomaly or birth defect
- An important medical event that may not result in death, be life threatening, or require hospitalization may be considered an SAE when, based upon appropriate medical judgment, the event may jeopardize the participant or may require intervention to prevent one of the outcomes listed in this definition.

8.2 Safety Assessment and Follow-Up

The subjects will be monitored for AEs and SAEs during the entire procedure and 30 minute monitoring window. All AEs, including observed or volunteered problems, complaints, signs or symptoms, and diagnoses, occurring from the initiation of Definity dosing until the completion of the Definity administration will be recorded on a serious or

non-serious AE data form, whether or not associated with the use of the trial medication.

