The use of an intravenous needle and the fluids given through the needle may cause minor discomfort, bleeding under the skin (bruise), fainting, and possible infection at the site of needle insertion. These risks are minimized by having nursing staff trained in placing IV lines perform these procedures in a safe, aseptic manner. The subjects' alternative is not to participate in this study and have only their scheduled clinical procedure(s) performed.

The invasive pressure measurement procedure (with 18G needle) has low risk similar to a stereotactic breast biopsy (mostly with 14G or larger needles). The risks includes: bruising and swelling of the breast, infection of the measurement site, and soreness at the needle injection. Also, there is low risk of infection and pain and they could be minimized by strict sterile technique and local lidocaine infiltration, respectively. The subjects' alternative is not to participate in the study.

1.4.2 **Benefits**

We do not expect any direct benefit for subjects enrolled in this study. The long-term benefits of this study will be the development of a noninvasive, safe, accurate IFP estimator. Additionally, it may lead to a novel functional predictor of malignancy in breast tumors.

2 **Study Objectives**

2.1 **Objectives**

This study is designed to compare the direct measurements of IFP in the breast tumor and its surrounding tissue with the values obtained from 3D SHAPE data (i.e., CEUS data).

2.1.1 **Primary**

The primary objective of the study is to determine if the 3D SHAPE results can be used to estimate IFPs in breast tumor and its surrounding tissue.

2.1.2 **Secondary**

The secondary objective of the study is to determine if the malignancy of breast tumor can be predicted by the 3D SHAPE results.

2.2 **Endpoints/Outcome Measures**

2.2.1 **Primary**

A Pearson's correlation coefficient above 0.5 will be considered a successful outcome.

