3.3 Duration of Therapy

The total infusion of Definity will be about 15 minutes.

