8.3 Recording Adverse Events

The following subsections detail what information must be documented for each adverse event occurring during the time period specified in Section 8.2 Safety Assessment and Follow-Up.

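### Section 8.2 monitors adverse events through the whole procedure but records them only during the Definity infusion, so the needle measurements and the 30-minute observation fall outside the recording rule

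*Combined protocol and SAP*

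**What the plan says.** Section 8.2 opens with the monitoring rule: "The subjects will be monitored for AEs and SAEs during the entire procedure and 30 minute monitoring window". The next sentence sets the recording rule, under which AEs "occurring from the initiation of Definity dosing until the completion of the Definity administration will be recorded" on a serious or non-serious AE form. That sentence applies regardless of any link to the trial drug, so it limits recording by time and not by cause.

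Section 8.3 requires relatedness, expectedness, severity and treatment to be documented for "each adverse event occurring during the time period specified in Section 8.2". It names no period of its own, and no other section sets a recording period.

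The order of the visit is given in the Study Summary schematic and in 3.1 and 6.3: infusion with imaging, a wait until Definity has cleared, a second imaging data set, local anesthesia, then one IFP needle measurement in the tumor and one in the surrounding tissue. Sections 3.4 and 6.3 start the 30-minute observation after the Definity administration.

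Section 1.4.1 says of the needle measurement: "The risks includes: bruising and swelling of the breast, infection of the measurement site, and soreness at the needle injection".

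**The concern.** One section holds two windows, and only the shorter one is attached to the AE form. The shorter window closes before local anesthesia, before both IFP punctures and before the observation period starts. Staff who followed the recording sentence to the letter would comply with the protocol while leaving needle-site events and delayed contrast reactions off the forms.

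The needle measurement supplies the reference values for the primary objective, and 1.4.2 expects no direct benefit to participants, so its harms deserve a complete record. Section 1.4.1 also warns of serious Definity reactions that arise after administration as well as during it. If some staff record later events and others do not, the AE counts will depend on who ran the visit. Events not written down on the day may not be recoverable afterwards.

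**Working it through.** The plan gives no figure for this point to reproduce. The check sets the sections against each other and against the timeline of the visit.

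**1. Which steps does each rule of 8.2 cover?**

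| Step (order from the schematic, 3.4 and 6.3) | Monitoring sentence | Recording sentence |
|---|---|---|
| Definity infusion | yes | yes |
| 30-minute observation after administration | yes | no |
| Clearance wait and second imaging data set | yes | no |
| Local anesthesia | yes | no |
| IFP measurement in tumor | yes | no |
| IFP measurement in surrounding tissue | yes | no |

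The observation period begins when administration ends, so it may overlap the steps listed below it. The recording sentence misses all of them either way.

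**2. How long is the recording window?**

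- Stated duration (3.3): "The total infusion of Definity will be about 15 minutes".
- Duration from volume and rate (5.3): "Two vials of Definity (3 ml in total) suspended in 50 ml saline will be administered as an IV infusion", at 4 to 10 ml/min. The volume is 3 + 50 = 53 ml. Time = volume / rate: 53/10 = 5.3 minutes and 53/4 = 13.25 minutes.
- Visit length (Study Summary): 80 to 90 minutes, including the 30 minutes of observation.
- Share of the visit, stated duration: 15/90 = 16.7% to 15/80 = 18.8%.
- Share of the visit, from volume and rate: 5.3/90 = 5.9% to 13.25/80 = 16.6%.

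The stated 15 minutes lies above the longest time that volume and rate allow. Those sections need to be reconciled, but the present point is the same under either.

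**3. Would extending recording to the end of the 30 minutes be enough?** With the stated duration the window becomes 15 + 30 = 45 minutes, or 45/90 = 50% to 45/80 = 56% of the visit. The plan does not say when within the visit the punctures occur or how long the clearance wait lasts. It is therefore not certain that both measurements fall within those 45 minutes, and the IFP step has to be named in the recording period.

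**4. What do the other sections imply?**

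- 8.1.2 defines an AE by its timing relative to research participation, not to drug exposure.
- 8.3.1 requires relatedness for all AEs and lists study procedures among the causes to consider.
- 8.4.2 sends all AEs and SAEs to the monitoring committee (DSMC).
- Appendix A marks AE assessment at the study visit, with no restriction to the infusion.

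All four fit the monitoring sentence. None fits a window that ends with the infusion.

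**5. Which events depend on the recording rule?** Under 8.4.1.1 and the DSMC table, Grade 1 and 2 events are reported at continuing review and at quarterly meetings, so they reach oversight through routine AE data. In 8.4.1.2, unexpected, related Grade 3-4 events and Grade 5 events are timed from knowledge of the event; 8.4.4 times FDA reports from receipt of the information. Those routes do not rest on the 8.2 window. The exposure is therefore mainly non-serious events.

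**The case against.** The strongest reply is that nothing forbids recording later events. Staff must watch the patient throughout, the AE definition is broad, and 8.3.1, 8.3.4, 8.4.2 and Appendix A all speak of AEs without an infusion limit. Section 8.3 points to a section with two periods, and the wider one can be read as the one meant. Serious events would still be reported through 8.4.1.2 and 8.4.4. Safety is not an objective or endpoint here, and the correlation analysis is unaffected.

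Most of this stands. A reader might infer that needle-procedure events can never be captured, or that the AE data must show none. The documents do not support that: they contain a conflict, and several sections lean towards fuller recording. A reader might also infer that the trial fails to prove its own description of the needle step as low risk. Section 1.4.1 offers that as background, by comparison with stereotactic biopsy, and the trial does not set out to test it.

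What the reply does not remove is that the only explicit recording rule is the narrow one. A wider intent inferred from other sections leaves recording to individual judgement.

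**Conclusion.** The point holds as an internal contradiction. Section 8.2 monitors over one period and records over a shorter one, and 8.3 does not say which governs. Read as written, the recording rule covers none of the 30-minute observation, none of the local anesthesia and neither of the two IFP measurements, for all 25 planned participants. The consequence is incomplete and possibly inconsistent AE forms and DSMC data, mainly for non-serious events. This assumes that staff follow the recording sentence literally; those who follow the monitoring sentence would lose less.

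Two stronger readings should be avoided. The window's share of the visit, about 6% to 19%, is a share of time and not of AEs missed; the plan gives no event rate for the needle step, so that share cannot be estimated. A reader might also infer that the 25% halting rule in 8.5 is disabled. That rule acts at scheduled interim analyses, the documents schedule none, and it only permits suspension, so no definite effect on it can be claimed.

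**What to change.** - Rewrite the recording sentence of 8.2 so that one period serves both monitoring and recording: the entire procedure, expressly including local anesthesia and both IFP measurements, plus the 30-minute observation. State where the procedure begins, because IV placement precedes dosing and 1.4.1 lists risks for it.
- Have 8.3 refer to that single period, and check that 8.1.2, 8.3.1, 8.4.2 and Appendix A agree with it.
- Attribute each AE to the contrast agent, the IFP procedure or the clinical biopsy. Section 8.3.1 already asks for study procedures to be considered; this makes the answer a recorded item.
- Record needle-site events reported after the visit when the team learns of them. Infection is a named risk in 1.4.1 and may appear later, so a cutoff at the end of the visit would still miss it.

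The cost is a short protocol amendment, slightly more AE recording and possibly a higher reported AE rate. Observation over this period is already required. The case report forms are held separately and could not be checked, so the size of any form change is not known. The change does not touch dosing, the length of observation or the primary analysis.

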Participant Participation Duration: The participation duration is about 80-90 minutes (including 30 minute-long monitoring time) in a single visit.

Estimated Time to Complete Enrollment: 15 months

Schematic of Study Design:

Prior to
Enrollment

Total 25: Obtain informed consent. Screen potential subjects by inclusion and exclusion criteria; obtain history, document.

Visit 1
On the day
Of a Biopsy

Conventional ultrasound imaging will be performed to examine the tumor followed by CEUS exam. Before collecting CEUS data, Definity will be administered IV and the acoustic settings will be optimized using a built-in software in a modified Logiq E9 or E10 scanner. The 3D SHAPE data will be collected using the determined acoustic settings during the infusion. Then, we wait for the clearance of Definity and another set of SHAPE data will be collected without Definity keeping the same acoustic settings.

The subject will have local anesthesia procedure and IFP will be measured from the breast tumor and its surrounding tissue using an 18G single-use needle connected to Stryker pressure monitoring system. The measurement procedure will be guided by ultrasound imaging. The measurements will be documented as well as their locations.

Compare the results from 3D
SHAPE data to IFP measurements
and find the correlation

1 Introduction

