1.4.1 Potential Risks

Serious cardiopulmonary and allergic reactions including fatalities have occurred during or following administration of Definity. However, these occurrences have been rare (less than 1 in 50,000 patients). As a result, patients with unstable cardiopulmonary conditions will be excluded. The majority of adverse events from Definity were mild to moderate in severity. Transient side effects that have been described as possibly related to Definity administration include headache (2.3%), back and renal pain (2.1%), flushing (1.1%) and nausea (1.0%). Hypersensitivity reactions to perflutren may occur, although extremely rare.

In a meta-analysis (which included 110,500 patients) [Khawaja et al. 2010] performed early after the FDA safety alerts in 2007, the incidence of serious allergic and anaphylactoid reactions immediately after the ultrasound contrast agent administration was estimated at 0.009% and 0.004%, respectively. These very rare but severe allergic reactions are secondary to a recently described variant of the type1 hypersensitivity reaction known as Complement Activation Related Pseudo Allergy, or CARPA reactions. [Szebeni 2005].

In a retrospective multicenter study, Wei et al [2008] reported on the safety of Definity (n=66164 doses) and Optison (n=12219 doses)- these included >10000 doses administered to critically ill patients in the intensive care unit or to patients with presumed ischemic chest pain. Severe reactions likely attributable to the contrast agents occurred in 8 patients (0.01%), and 4 of these were anaphylactoid reactions. Interestingly, all of the severe reactions occurred in outpatients, indicating that the FDA warning on contrast administration in patients with severe cardiopulmonary conditions likely would not have mitigated risk in these patients.

CARPA reactions may be mild to moderate (sneezing, tingling sensation, urticaria, or pruritis) or severe (wheezing, angioedema, cyanosis, and anaphylactic shock). CARPA

reactions seem more common when a large bolus of lipid shelled contrast agent is injected, and slow continuous infusions of diluted contrast likely afford significant protection against these reactions.

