3.4 Duration of Follow Up

All participants will have a 30-minute monitoring period after the administration of Definity.

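### Section 8.2 gives two conflicting adverse-event windows: monitoring covers the whole visit, but the recording sentence stops when Definity administration ends

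*Combined protocol and SAP*

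**What the plan says.** Section 8.2 sets two periods in consecutive sentences. The first concerns watching: "The subjects will be monitored for AEs and SAEs during the entire procedure and 30 minute monitoring window". The second concerns what goes on the AE form, namely events "occurring from the initiation of Definity dosing until the completion of the Definity administration will be recorded".

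Section 8.3, which governs relatedness, expectedness, severity and treatment, sets no period of its own. It describes "what information must be documented for each adverse event occurring during the time period specified in Section 8.2 Safety Assessment and Follow-Up".

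Three other places fix what happens once the infusion is over:

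- Section 3.4: "All participants will have a 30-minute monitoring period after the administration of Definity".
- Schematic of Study Design, after the contrast acquisition: "Then, we wait for the clearance of Definity and another set of SHAPE data will be collected without Definity". The anesthesia and needle measurements come after that.
- Section 6.3: "Local anesthesia procedures will be performed using simple Lidocaine 1%, or combined with 1:100,000 Epinephrine (EPI) before the IFP measurements", followed by "Take a single IFP measurement each from the breast tumor and its surrounding tissue".

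**The concern.** The recording sentence is the working rule, because it tells staff which events to write down. As worded, it closes before two sources of risk that the protocol itself names.

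The first is delayed reaction to the contrast agent. Section 1.4.1 warns: "Serious cardiopulmonary and allergic reactions including fatalities have occurred during or following administration of Definity". The 30-minute period presumably exists to catch the later ones, yet all of it lies after the recording window has closed.

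The second is the research needle. Section 1.4.1 lists bruising, swelling, infection and soreness among its risks, and Section 1.4.2 expects no direct benefit to participants. Every event from the anesthetic or the 18G needle would start after recording has stopped.

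At stake is the completeness and consistency of the safety record. Two careful coordinators could each follow a different sentence of Section 8.2 and produce different AE counts from the same participants.

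**Working it through.** The plan has no figure to reproduce here. The check is a timeline, with a little arithmetic to size the two windows.

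**Inputs**

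- Infusion: about 15 minutes (Section 3.3).
- Volume and rate: 3 ml Definity in 50 ml saline at 4 to 10 ml/min (Section 5.3).
- Monitoring after Definity: 30 minutes (Sections 3.4 and 6.3).
- Visit length: about 80 to 90 minutes (Study Summary).
- Participants: 25 (Section 3.2). IFP measurements: one in the tumor and one in surrounding tissue (Section 6.3).

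**Order of events** (Schematic of Study Design and Section 6.3): baseline ultrasound; Definity infusion with SHAPE acquisition; wait for clearance; second SHAPE acquisition; local anesthesia; IFP measurements. The 30-minute period starts when administration ends and may overlap the later steps.

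**Length of the recording window.** As stated, about 15 minutes. From volume and rate, (50 + 3)/10 = 5.3 minutes to (50 + 3)/4 = 13.25 minutes. The stated 15 minutes is used below because it is the more generous figure.

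- Share of infusion plus monitoring: 15/(15 + 30) = 33%.
- Share of the visit: 15/90 = 17% to 15/80 = 19%.

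**What each sentence covers**

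| Item | Recording sentence | Monitoring sentence |
|---|---|---|
| Post-Definity minutes per participant | 0 of 30 | 30 of 30 |
| IFP measurements (2 x 25 = 50) | 0 of 50 | 50 of 50 |

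These counts show how far apart the two readings are. They do not estimate missed events: the documents give no rate or onset time for needle-site events.

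**Does another section settle it?**

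- Section 8.1.2 defines an AE by its timing relative to taking part in the research. This is broad, but it is a definition and not a recording period.
- Section 8.3.1 requires study procedures to be considered as a cause. This implies that needle events count, but Section 8.3 takes its period from 8.2.
- Section 8.4.2 sends all AEs and SAEs to the DSMC. This acts on events already known and sets no period for recording them.
- Appendix A marks AE assessment at the study visit, in the same column as the IFP measurements. This is the best support for a wider window, but it does not say when in the visit recording ends.

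None of these says that events after the infusion will be recorded.

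**The case against.** The strongest reply is that this is a slip in one clause and not a plan to ignore the needle. The monitoring sentence, the broad AE definition, the instruction to consider study procedures, the DSMC rule and the Appendix A row all point to the whole visit. Staff told to watch for AEs would probably write down what they saw. The case report forms are held separately from the protocol and were not available; they may already carry the wider window. Most of this stands. It means that the documents support an inconsistency, but not a prediction that events would go unrecorded. It does not remove the need to correct the sentence, because no other text overrides it.

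A reader might also infer three stronger points, which the documents do not support:

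- **That the lack of AE follow-up after the visit is itself an error.** It is true that Appendix A has no later column and that Section 6.4 collects only biopsy results. But this is a single-visit pilot, Section 1.4.1 rates the needle as low risk and similar to a stereotactic biopsy, and a clinical biopsy is due the same day, so later site events would be hard to attribute. The reporting rules in Section 8.4 set no onset cut-off, so a later event that came to light could still be reported. Active follow-up is a debatable design choice.
- **That the 25% halting rule is undermined.** Section 8.5 applies at scheduled interim analyses, but the available text gives no schedule for them, and enrollment only may be suspended. Any effect is speculative.
- **That the study's conclusions are at risk.** The correlation and malignancy analyses do not use AE data.

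**Conclusion.** The concern holds as a conflict within Section 8.2 that other sections hint at resolving but do not resolve. Read literally, the recording rule covers about 15 minutes of an 80 to 90 minute visit, none of the 30 monitoring minutes, and none of the 50 needle measurements. Read with the monitoring sentence, it covers all of them.

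This rests on the order of procedures in the Schematic and Section 6.3, and on the 30-minute period starting when administration ends, as Section 3.4 says. It assumes no event rate and claims no number of lost events. Confidence is high that the two windows differ, and lower about what staff would do in practice. The correction is worth making because it only aligns recording with the monitoring that the protocol already promises.

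**What to change.** Amend the recording sentence in Section 8.2 so that AEs are recorded from the start of Definity dosing through the last IFP measurement or the end of the 30-minute monitoring window, whichever is later. Section 8.3 then follows a single stated period, and the AE row in Appendix A can stay as it is. Check that the AE form uses the same period.

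The cost is a one-sentence protocol amendment, which needs IRB approval under Section 14.2. Recorded AE counts may rise slightly. No visit or procedure is added.

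Optionally, and separately from this correction, the sponsor could add one chart check per participant (25 in all) for documented needle-site events when the biopsy result is collected. That would also mean changing Section 6.4 and Appendix A. It would miss mild unreported events and could not reliably separate the research needle from the biopsy. The documents give no basis for choosing how many days it should cover.
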